We have recently initiated a phase II randomized trial comparing decitabine to azacitidine given in an abbreviated way of 3 days in patients with low-risk MDS. So far, 34 patients were enrolled (19 treated with azacitidine and 15 with decitabine). 24 patients are evaluable for response. The response rates were 31% and 36% for patients treated with azacitidine and decitabine respectively with no significant toxicity.

Given our previous experience and considering the above data in support of lower doses regimen we propose to evaluate in a phase II Bayesian design the efficacy of DAC versus AZA versus standard AZA (5 days) in patients with low and intermediate-1 risk MDS transfusion-dependent versus BSC in patients with low and intermediate-1 risk MDS transfusion-independent .

III. BACKGROUND DRUG INFORMATION

A. Decitabine:

Decitabine (Dacogen™, 5-aza-2'-deoxycytidine) is an analogue of the natural nucleoside 2'- deoxycytidine. It is believed to exert its antineoplastic effects after phosphorylation and direct incorporation into DNA and inhibition of DNA methyltransferase, causing hypomethylation of DNA and cellular differentiation or apoptosis. Decitabine inhibits DNA methylation *in vitro*, which is achieved at concentrations that do not cause major suppression of DNA synthesis. In rapidly dividing cells, the cytotoxicity of decitabine may also be attributed to the formation of covalent adducts between DNA methyltransferase and decitabine incorporated into DNA. Non-proliferating cells are relatively insensitive to decitabine.

In solid tumor patients who received 72-hour infusion of decitabine at 20 to 30 mg/m²/day, decitabine pharmacokinetics were characterized by a biphasic disposition. The total body clearance (mean \pm SD) was 124 \pm 19 L/hr/m², and the terminal phase elimination half-life was 0.51 \pm 0.31 hr. The exact route of elimination and metabolic fate of decitabine is not known in humans. One of the pathways of elimination of decitabine appears to be deamination by cytidine deaminase found principally in the liver but also in granulocytes, intestinal epithelium and whole blood. *In vitro* studies in human liver microsomes suggest that decitabine is unlikely to inhibit or induce cytochrome P450 enzymes. *In vitro* metabolism studies have suggested that decitabine is not a substrate for the human liver cytochrome P450 enzymes. As plasma protein binding of decitabine

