Supportive measures such as prophylaxis for tumor lysis syndrome, analgesics, blood transfusions, antimicrobials and G-CSF for fever/infection are permitted as clinically indicated. Growth factor and ESA administration while on study will be documented.

VII. STUDY END POINTS

Primary:

1. Event-free survival rates of two different drugs DAC versus AZA on an abbreviated schedule and a standard arm of AZA given over 5 days in patients with low-risk MDS transfusion-dependent and to BSC in patients with low-risk MDS transfusion-independent. Events are defined as no response, loss of response, progression to higher risk category MDS, transformation to AML, discontinuation of therapy due to side effects, or death.

Secondary:

1. Overall improvement rate (OIR), defined as complete remission (CR), partial remission (PR), marrow CR (mCR), or hematologic improvement (HI), measured using each patient's best response with the 2 different agents. Response will be

assessed using the modified MDS International Working Group 2006 criteria. The best response within the first two cycles will be the OIR for each treatment arm that will be used in the adaptive randomization algorithm.

2. Transfusion independence (defined as being transfusion-free for ≥ 8 consecutive weeks between the first dose and study treatment discontinuation)
3. Cytogenetic response, if applicable
4. Clinical benefit
5. Duration of response
6. Time to transformation into AML
7. Overall survival
8. Safety profile

VII. CRITERIA FOR WITHDRAWAL

Reasons for withdrawal include:

- Withdrawal of consent or the subject refuses to continue treatment and/or procedures/observations.
- Relapse/progression unless the treating physician determines that the patient has achieved clinical benefit, at which time further therapy on protocol may be permitted with approval from the PI and the discussion documented in the patient's medical record.
- No response after at least 6 courses unless the treating physician determines that the patient has achieved clinical benefit, at which time further therapy on protocol may be permitted with approval from the PI and the discussion documented in the medical

record. A bone marrow biopsy and/or aspirate is required to confirm that the patient has not achieved a response.

- Intercurrent illness preventing further administration of protocol treatment,
- Unacceptable toxicity that in the opinion of the investigator makes continued therapy unsafe.

VIII. CRITERIA FOR RESPONSE

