The response criteria recommended by the MDS International Working Group 2006.

Responses must be verified, documented, and signed in the local medical record by the local PI. (Patients are considered non evaluable if they have received less than 2 courses of treatment, unless there is clear disease progression.)

Definitions:

Complete Response (CR):

Bone marrow: $\leq 5\%$ myeloblasts with normal maturation of all cell lines; persistent dysplasia will be noted

Peripheral blood:

Hgb ≥ 11 g/dL

Platelets $\geq 100 \times 10^9/L$

Neutrophils $\geq 1.0 \times 10^9/L$

Blasts 0%

Partial response (PR):

All CR criteria if abnormal before treatment except: bone marrow blasts decreased by $\geq 50\%$ over pretreatment but still $> 5\%$

Marrow CR:

Blasts \leq 5% and decrease by \geq 50% from baseline (baseline blasts should be above 5% to be eligible for marrow CR)

Hematologic Improvement (HI): (responses must last at least 8 weeks)

Erythroid response [HI-E; (if pretreatment Hgb $<$ 11 g/dL)]; Hgb increase by \geq 1.5 g/dL; Relevant reduction of units of RBC transfusions by an absolute number of at least 4 RBC transfusions/8 weeks compared with the pretreatment transfusion number in the previous 8 weeks. Only RBC transfusions given for a Hgb of \leq 9.0 g/dL pretreatment will count in the RBC transfusion response evaluation.

Platelet response [HI-P; ((if pretreatment Platelet count $<$ $100 \times 10^9 /L$)]: Absolute increase of $\geq 30 \times 10^9 /L$ for patients starting with $> 20 \times 10^9 /L$ platelets, or increase from $< 20 \times 10^9 /L$ to $> 20 \times 10^9 /L$ and by at least 100%.

Neutrophil response [HI-N; (pretreatment, ANC $< 1.0 \times 10^9 /L$)]: At least 100% increase and an absolute increase $> 0.5 \times 10^9 /L$

Progression/Relapse after hematological improvement: ≥ 1 of the following: $\geq 50\%$ decrement from maximum response levels in granulocytes or platelets; \downarrow in Hgb by ≥ 1.5 g/dL; transfusion dependence

Stable Disease: Not satisfying criteria for Complete Remission, Partial Response, Marrow CR, Hematologic Improvement or Progression/Relapse.

IX. REPORTING REQUIREMENTS

All adverse and serious adverse events will be recorded and reported according to the Leukemia-Specific Adverse Events (appendix A). The MD Anderson Leukemia

Department will report SAEs in accordance with MD Anderson IRB policies and procedures and Appendix A of the protocol.

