Patients will be randomized using a Bayesian adaptive algorithm. Patients will be randomized fairly among the three arms at the start of the trial (for the first 30 patients), that is, 10 patients per arm. Thereafter, as the trial progresses and data accrue, the randomization will become unbalanced in favor of the treatment that, on average, has better results in terms of event free survival. Therefore, each successive patient is more likely to receive the treatment with better results, on average. A minimum of 30 and a maximum of 150 patients will be accrued. There will be 12 months follow up after the last patient is accrued with an anticipated accrual rate of 5 patients per month.

Denote the event free survival for the patients in the three arms (DAC; AZA3; AZA5) as T_i for $i=1,2,3$. Assume the T_i is independent exponential with median μ_i . And each μ_i independently follows an inverse gamma distribution with parameter $\alpha=2.05$, $\beta=7.34$. The parameters were chosen to set the mean of the prior equal to 7 (the historical median EFS in months) and a variance of 1000. For each patient, the randomization probability for treatment arm i will be based on the posterior probability that it has the largest median EFS. For example, for arm 1, the posterior probability is $\pi_1=\Pr(\mu_1 > \mu_i)$ for $i=2,3$. In order to avoid aggressively favoring one arm too early in a large trial, instead of

assigning patients with posterior probability, we use its square root transformation as in the following formula to assign patients:

$$Aa = \frac{\sqrt{\pi_1}}{\sqrt{\pi_1} + \sqrt{\pi_2} + \sqrt{\pi_3}}, \text{ where } Aa \text{ is the probability of assigning patients to arm 1, } \pi_1 \text{ is}$$

the posterior probability that arm 1 is superior, etc.

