Data analysis will be performed using SAS or S-plus, as appropriate. All patients will be included in the intent-to-treat analysis for efficacy. Demographic and disease characteristics of the patients at registration will be summarized using descriptive statistics such as mean, standard deviation (SD), median and range. The EFS under different treatment will be estimated by Kaplan-Merier method, along with the 95% credible intervals, and logrank test will be used to assess the EFS differences under different treatments. The Cox proportional hazards model will be used to analyze the effects of treatments and other covariates.

Figure 1. Survival of Patients with Low Risk MDS According to the Lower Risk Prognostic Model

[figure not shown]

Table 9. Prognostic Model of Lower-Risk Myelodysplastic Syndrome: Multivariate Analysis Poor-Prognosis Parameters and Assigned Score

Adverse Factor *P* Assigned Score

Unfavorable cytogenetics < .001 1

Age \geq 60 years < .001 2

Adverse Factor	P	Assigned Score
Hgb < 10 g/dL	< .001	1
Plt, $\times 10^9/L$		
< 50	< .001	2
50-200	< .001	1
BM blasts $\geq 4\%$	< .001	1

Table 10. Prognostic Model of Lower-Risk Myelodysplastic Syndrome: Estimated Survival Outcome Within Each Score Range

Score	No. of Patients	Median Survival (months)	4-Year Survival Rate (%)
0	11	NR	78

Score No. of Patients Median Survival (months) 4-Year Survival Rate (%)

1	58	83	82
2	113	51	51
3	185	36	40
4	223	22	27
5	166	14	9
6	86	16	7
7	13	9	NA

XI. References:

1. Nimer SD (2008) Myelodysplastic syndromes. *Blood* 111:4841–4851.

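### The two-course evaluability rule and the all-patients ITT statement are not reconciled for the response rate (OIR); the ordinary reading drops early failures other than progression

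*Combined protocol and SAP*

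**What the plan says.** Section VIII (Criteria for Response) sets an evaluability rule: "Patients are considered non evaluable if they have received less than 2 courses of treatment, unless there is clear disease progression".

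The Analysis Plan in section XII says, without exception: "All patients will be included in the intent-to-treat analysis for efficacy".

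Section VII (Study End Points) lists OIR as the first secondary endpoint. It is CR, PR, marrow CR or hematologic improvement, "measured using each patient's best response with the 2 different agents". No denominator is given. Nothing in the documents says that non-evaluable patients count as non-responders, or that an evaluable set is only supplementary.

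Two further statements bear on how far the rule reaches:

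- Section VII adds: "The best response within the first two cycles will be the OIR for each treatment arm that will be used in the adaptive randomization algorithm". The Design text of both parts of section XII says instead that "the randomization will become unbalanced in favor of the treatment that, on average, has better results in terms of event free survival".
- The EFS events in section VII include "discontinuation of therapy due to side effects, or death".

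Section II (Rationale) reports the team's earlier trial of the 3-day regimens. It had enrolled 34 patients (19 azacitidine, 15 decitabine), of whom "24 patients are evaluable for response", with response rates of 31% and 36%.

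**The concern.** The rule is asymmetric. A patient who progresses during course 1 is kept and counts as a failure. A patient who stops in course 1 for toxicity, intercurrent illness or withdrawal, or who dies without progression, becomes non evaluable. Few of these can be responders, because the first on-treatment marrow comes after cycle 2 and hematologic improvement must last at least 8 weeks. Removing them shrinks the denominator and leaves the numerator almost untouched.

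Whether a patient reaches course 2 is a post-randomization outcome that treatment can influence. The arms differ in drug and in number of dosing days, so equal early loss cannot be taken for granted. The response comparison would then partly reflect who stayed on treatment rather than who responded.

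BSC raises a further difficulty. BSC patients receive no courses, so read literally none is evaluable unless the disease progresses. Yet comparing response among transfusion-independent patients is a stated secondary objective.

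**Working it through.** **1. The earlier trial's figures.** Inputs from section II: 34 enrolled (19 and 15), 24 evaluable, rates 31% and 36%. I searched all splits of 24 with at most 19 on azacitidine and at most 15 on decitabine, and all whole numbers of responders, for rates within 1 point of those stated. One combination fits:

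- azacitidine 4/13 = 30.8%
- decitabine 4/11 = 36.4%

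The published rates are therefore consistent with an evaluable-only denominator, which leaves out 34 − 24 = 10 patients (10/34 = 29%).

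**2. The same data on all enrolled**, assuming none of the 10 responded:

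| | Evaluable | All enrolled | Share non evaluable |
|---|---|---|---|
| Azacitidine | 4/13 = 30.8% | 4/19 = 21.1% | 6/19 = 32% |
| Decitabine | 4/11 = 36.4% | 4/15 = 26.7% | 4/15 = 27% |
| Difference | 5.6 points | 5.6 points | |

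Each arm falls by about 10 points, but the gap between arms does not move, because the non-evaluable shares were similar.

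**3. Effect of unequal loss in this trial.** Let p be the true all-patient response rate and q the share non evaluable, all of them non-responders. Then:

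reported rate = p / (1 − q)

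The documents give no q by arm, so these values are assumptions. Take p = 31% in both arms and q = 5% in the reference arm, which gives 0.31/0.95 = 32.6%.

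| q in the other arm | Reported rate | Spurious gain |
|---|---|---|
| 10% | 0.31/0.90 = 34.4% | 1.8 points |
| 20% | 0.31/0.80 = 38.75% | 6.1 points |
| 30% | 0.31/0.70 = 44.3% | 11.7 points |

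On an all-randomized denominator the gain is 0 in every row.

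**4. Break-even.** If the reference arm has p = 36% and q = 5%, it reports 0.36/0.95 = 37.9%. An arm with q = 20% reports the same figure when its all-patient rate is only 0.379 × 0.80 = 30.3%. With q = 30% it needs only 0.379 × 0.70 = 26.5%.

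**5. If OIR were used for allocation.** This is a two-arm illustration by simulation (4,000 trials). It assumes 40 patients per arm (close to Table 3, scenario 1), a true rate of 31% in both, Beta(1,1) priors and q = 5% in the reference arm. The average posterior probability that the arm with more early loss is better is about 0.55, 0.64 and 0.74 for q = 10%, 20% and 30%. With all patients counted it is 0.50.

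**The case against.** **Non evaluable need not mean excluded.** It may be only a response label, with the ITT sentence fixing the denominator. The two statements can be read that way. But the documents do not say so, exclusion is the ordinary meaning, and the earlier trial's rates fit only an evaluable denominator. The ambiguity needs settling on either reading.

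**A reader might infer that the rule favours the more toxic arm.** The documents do not establish this. They give no early-stopping rates by arm and report no significant toxicity with the 3-day regimens. They also allow course 2 despite myelosuppression, which removes one reason for stopping early. The toxicity monitoring limits how far toxicity alone could drive loss: at a true rate of 30%, Tables 5 and 8 give early-stopping probabilities of 0.94 and 0.88. At 20% these are only 0.25 and 0.28, and withdrawal, intercurrent illness and unrelated death are not monitored that way. The direction of bias therefore remains conditional on unequal loss.

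**A reader might take the earlier trial as proof of a 10-point inflation.** That trial was still enrolling, and the reasons for non-evaluability are not given. Some of the 10 patients may simply have been too early to assess. Nor is it stated that the trial used this two-course rule. Its data show no distortion between arms.

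**The primary analysis is protected.** This stands. EFS counts stopping for side effects and death as events. Section XII bases allocation, arm dropping, early stopping and final selection on median EFS, and Tables 3 and 6 simulate EFS only.

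**Conclusion.** The point holds for OIR as a secondary endpoint. The plan states a specific, asymmetric evaluability rule and a general all-patients ITT statement, and does not say which applies to response. On the ordinary reading, OIR is inflated in every arm. The comparison between arms is biased only if early loss without progression differs by arm. Under the assumed losses the spurious gain runs from 1.8 points (10% against 5%) to 11.7 points (30% against 5%); the lower end is small. These figures rest on a 31% all-patient rate and on those dropped being non-responders.

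Two stronger readings are not supported. Not every early death leaves the denominator, since a patient with clear progression stays evaluable. And the rule does not reach the adaptive randomization under the algorithm in section XII, which runs on EFS. It would do so only if the conflicting sentence in section VII were followed.

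**What to change.** 1. State in the Analysis Plan that OIR is analysed on all randomized patients by arm. Patients with fewer than two courses and no documented response count as non-responders.
2. Keep the evaluable-only rate as a labelled sensitivity analysis, and report by arm the number of non-evaluable patients and the reasons.
3. Define response evaluability for BSC patients by time on study, since a count of courses cannot apply to them.
4. Reconcile the section VII statement that the two-cycle OIR enters the adaptive randomization with the EFS-based algorithm in both parts of section XII. If OIR is retained there, use the all-randomized denominator.

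The cost is SAP and protocol wording. Reported response rates become somewhat lower, and they will not compare directly with evaluable-only rates such as those of the earlier trial; the sensitivity analysis keeps that comparison available.

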- Sign an IRB-approved informed consent document.
- Age ≥ 18 years.
- IPSS low- or intermediate-1–risk MDS, including CMML-1
- ECOG performance status of ≤ 3 at study entry.
- Organ function as defined below:
 - Serum creatinine ≤ 2 mg/dL
 - Total bilirubin $\leq 2 \times$ ULN
 - ALT (SGPT) $\leq 2 \times$ ULN
 - AST (SGOT) $\leq 2 \times$ ULN

- Women of childbearing potential must have a negative serum or urine pregnancy test within 7 days and will also need to use contraceptives. Men must agree not to father a child and agree to use a condom if his partner is of child bearing potential.

Exclusion Criteria:

- Breast feeding females
- Prior therapy with decitabine or azacitidine

V. Treatment plan

1. Study design

Transfusion-dependent subjects will be randomized to AZA 75 mg/m² IV/SC for 5 days, AZA 75 mg/m² IV/SC for 3 days, or DAC 20 mg/m² IV for 3 days on an even basis at the beginning, then, based on efficacy and following a Bayesian design, patients will be assigned to the superior arm.

Transfusion-independent subjects will be randomized to either BSC or one of the 3 arms mentioned above on an even basis at the beginning, then, based on efficacy and following a Bayesian design, patients will be assigned to the superior arm.

Transfusion-independent subjects assigned to BSC will be assigned to one of the 3 above arms once they start requiring blood transfusion. That would be considered an event.

Transfusion-dependent group will be defined as patients requiring blood transfusion for MDS or CMML-1 at any time.

2. Treatment plan

Patients will be randomized to receive:

Decitabine 20 mg/m² IV daily for 3 days (days 1-3) approximately every 28 days

or

Azacitidine 75 mg/m² SC or IV daily for 3 days (days 1-3) approximately every 28 days

or

Azacitidine 75 mg/m² SC or IV daily for 5 days (days 1-5) approximately every 28 days

or

BSC (for transfusion-independent subjects only)

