2. Creatinine, bilirubin, ALT or AST once monthly prior to start of each cycle.
3. Bone marrow aspirate and/or biopsy to confirm response, to be performed after cycle 2 then every 3 cycles for the first year, then every 6 cycles thereafter.
All bone marrows will be performed by the registering center, not in the local MD office.
4. Conventional cytogenetics to be performed after cycle 2 then every 3 cycles for the first year, then every 6 cycles thereafter
5. Documentation of frequency of transfusions (PRBC and Platelets) prior to start of each cycle.
6. Documentation in the medical record of any grade 3 or higher possibly, probably, definitely related adverse events that have occurred prior to start of each cycle. For guidelines on SAE Reporting and AE entry for Case Report

Forms (CRF), please refer to Appendix A (for MD Anderson) and Appendix G (for Participating Institutions).

7. Documentation of any prior administration of growth factors and ESA prior to start of each cycle

Table 2: Evaluation

Test	Pre-treatment	During treatment
CBC, differential platelet count	within 14 days of treatment start	Monthly prior to start of each cycle (+/- 7 days)
Creatinine, bilirubin, ALT or AST	within 14 days of treatment start	Monthly prior to start of each cycle (+/- 7 days)
Bone marrow aspirate	Within 6 weeks prior to study entry	after cycle 2 then prior to every 3 cycles for the first year, then prior to every 6 cycles thereafter
Cytogenetics	Within 3 months prior to study entry	after cycle 2 then prior to every 3 cycles for the first year, then prior to every 6 cycles thereafter
Serum or urine pregnancy test for woman of childbearing potential	within 7 days of treatment start	
Transfusion history documented	Prior to study entry	Prior to start of each cycle
Growth factors and ESA documentation	Prior to study entry	Prior to start of each cycle

Follow-Up

Following completion of active treatment and while still on study, patients will be followed for survival approximately every 6 to 12 months for up to 5 years. This follow up can either be done as a visit to the study doctor's clinic or via telephone call to the patient.

Chemotherapy administration

If the study doctor decides it is acceptable, enrolled subjects may be allowed to receive treatment from their local cancer doctor following cycle 1 (appendix B). However, enrolled subjects will have to return to the study doctor's clinic at least every 3 cycles for study visits.

Supportive care

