This is an adaptive randomized phase II trial for low-risk MDS patients. Regarding the patients transfusion status, patients can be categorized as transfusion dependent and transfusion independent patients. It is expected that there will be half of the transfusion-dependent patients and half of transfusion-independent patients. For transfusion dependent patients, the goal is to compare three treatment arms: 1) DAC, 2) AZA3 (treatment of 3 days), and 3) AZA5 (treatment of 5 days). For transfusion independent patients, the goal is to compare four treatment arms: 1) best supportive care (BSC) 2) DAC, 3) AZA3 (treatment of 3 days), and 4) AZA5 (treatment of 5 days). The primary outcome is event free survival (EFS) defined as the time from beginning of treatment till an event occurs or last follow-up. For transfusion independent patients, the events includes lack of response, requirement of blood transfusion, progression to advanced stages of disease, transformation into AML, discontinuation of therapy due to side effects, and death. The patients who change from transfusion independence to transfusion dependence under BSC will be enrolled in transfusion-dependent group and adaptively assign to the three treatment arms, that is, DAC, AZA3, or AZA5. For transfusion dependent patients, the events includes lack of response, progression to advanced stages of disease, transformation into AML, discontinuation of therapy due to side effects, and death.

Study design

The maximum number of patients accrued will be 240. There will be two parallel adaptive randomization trials for transfusion dependent (N=120) and transfusion independent (N=120) patients respectively. Since we are expecting patients under BSC

will eventually become the transfusion dependent, it is assumed that initially there will be 120 patients under transfusion-dependent group, and the total number increases to about 150 after enrolling the approximate 30 patients under BSC.

Part I Transfusion dependent patients (N=150)

Design

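### In Part II, lack of response is an EFS event with no date, rule or time origin for best supportive care; if that arm is exempt, only the drug arms are charged with non-response

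*Combined protocol and SAP*

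**What the plan says.** Section XII (General Description) names four arms for transfusion-independent patients, BSC among them, and gives them one event list with no exception: "For transfusion independent patients, the events includes lack of response, requirement of blood transfusion, progression to advanced stages of disease", followed by AML, discontinuation for side effects and death. EFS is "defined as the time from beginning of treatment till an event occurs or last follow-up". Section VII (Study End Points) has a different list: "Events are defined as no response, loss of response, progression to higher risk category MDS". It includes loss of response, omits transfusion, and gives no date for non-response.

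The passages that bear on response all count drug cycles or courses:
- Section VI, During therapy: "Bone marrow aspirate and/or biopsy to confirm response, to be performed after cycle 2 then every 3 cycles for the first year".
- Section VII, secondary endpoint 1: "The best response within the first two cycles will be the OIR for each treatment arm". The sentence goes on to say that this rate feeds the adaptive randomization.
- Criteria for Withdrawal: non-response is acted on after at least six courses, with an exception for clinical benefit.
- Section VIII: "Patients are considered non evaluable if they have received less than 2 courses of treatment", unless there is clear progression.

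Section VIII also keeps a separate category: "Stable Disease: Not satisfying criteria for Complete Remission, Partial Response, Marrow CR, Hematologic Improvement or Progression/Relapse". No passage says whether stable disease is a failure for EFS.

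The only rule written specifically for BSC is in Section V: "Transfusion-independent subjects assigned to BSC will be assigned to one of the 3 above arms once they start requiring blood transfusion". The next sentence makes that an event.

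**The concern.** A BSC patient who stays stable and untransfused is not a responder under Section VIII. One analyst could code that patient as failed for lack of response and another as event-free, and both would be following the plan. If the patient is coded as failed, no passage supplies the failure date, and no start of treatment exists from which to count.

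This matters because comparison with BSC is part of the primary objective. Section XII uses EFS for allocation, arm dropping and selection, and the Analysis Plan uses it for the log-rank test. At the response rates quoted in the Rationale, non-response could be the most frequent event in a drug arm, so the choice can decide the direction of the result.

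**Working it through.** **The plan's own figures.** The Part II prior is inverse gamma (2.14, 13.73). Its mean is 13.73/1.14 = 12.04 and its variance is 13.73²/(1.14² × 0.14) = 1036, against the stated 12 and 1000. A simulation without the lack-of-response clause, with single-exponential EFS and arms suspended and reopened as Part I describes, selects the best arm in scenario 5 in 80.1% of trials (Table 6: 79.7%) and each arm in scenario 1 in 2.7–3.7% (Table 6: 2.9–3.7%). Table 6 is thus reproduced by a smooth exponential with no cluster of failures at a response landmark.

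**Inputs for the illustration.**
- Drug response: 23% (decitabine), 31% (azacitidine) and 36% (decitabine), from the Rationale. Transfusion status is not stated there, and the last two rest on 24 evaluable patients.
- Background median for all other events: 12 months, the Part II historical figure, assumed equal in all arms.
- Candidate dates with 28-day courses: 6 × 28/30.4375 = 5.52 months and 2 × 28/30.4375 = 1.84 months. The two-cycle date is an inference; that window defines a secondary endpoint.

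**Reading 1: BSC exempt.**

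The event-free share just past date t is p × S(t) in a drug arm and S(t) on BSC, where p is the response rate and S(t) = 2^(−t/12). S(5.52) = 0.727.
- Drug arm: 0.23 × 0.727 = 0.167 to 0.36 × 0.727 = 0.262.
- BSC: 0.727.

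Log-rank simulation: BSC against one drug arm, 30 per arm (120/4), 30 months of accrual (120 at 4 per month) plus 12 months, 33% response, two-sided 5%, 1,000 runs per setting. BSC is significantly better in roughly 60–84% of trials over the two dates. Without the clause the figure is about 3% in each direction. If half of the non-responders are excused, it is 22–29%.

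Now let the drugs double the median time to every other event, to 24 months, with 36% response. The exponential-fit median is ln2 × [(1−p)(1−e^(−λt))/λ + p/λ], with λ = ln2/24.
- t = 5.52: 0.693 × (0.64 × 5.10 + 12.47) = 10.9 months.
- t = 1.84: 0.693 × (0.64 × 1.79 + 12.47) = 9.4 months.

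Both lie below 12 on BSC. The result depends on p: at six courses it is 8.2 months for 23%, 9.9 for 31% and 13.8 for 50%.

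**Reading 2: the clause applies to BSC on the same date.**

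All arms then face one rule. With 0% response on BSC (an assumption; the plan gives no rate) and 33% on drug, BSC is significantly worse in 32–71% of trials. At 20% BSC response this falls to 8–10%, and at equal response it is about 3% each way. This is a response effect.

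The reading does not fit the 12-month reference. Ten BSC failures at 5.52 months give a posterior of inverse gamma (2.14 + 10, 13.73 + 0.693 × 55.2) = (12.14, 51.99). Then Pr(median > 12) = 0.0015, far below the 0.1 dropping threshold.

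**The case against.** Much of the case on the other side stands.

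- A reader might infer that the whole primary comparison with BSC is undefined. The documents do not support that. Transfusion need (Sections V and XII), progression, AML and death can all be observed on BSC. What is missing is one component, its date and the time origin.
- A reader might infer that either coding makes the comparison unfair. Only exemption does. A clause applied to every arm on the same date is symmetric, and a difference caused by unequal response is a treatment effect on a listed component.
- The two readings are not equally likely. Section XII expects BSC patients to become transfusion dependent eventually, with about 30 moving to Part I, and uses a 12-month reference. Both fit follow-up to transfusion better than mass failure at a landmark. This favours exemption, which is the biased reading.
- The six-course rule excuses clinical benefit. It governs withdrawal and is not carried into the EFS definition. If it were, a 12-month drug-arm median would need 22–35% of non-responders excused if there were no other events, since (0.5 − p)/(1 − p) is 0.35 at p = 0.23 and 0.22 at p = 0.36. With a 24-month background it would need 54–62%.
- The adaptive consequences cannot be put in one number. With BSC exempt, equal 12-month backgrounds and 33% response, BSC is selected in 33–66% of simulated trials under the suspension rule that tracks Table 6. Under Part II's written rule, which stops the trial when any arm falls below 0.025, it is selected in 0–10%. Neither figure recalculates Table 6's 3.7%, whose null is equal median EFS.

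**Conclusion.** The concern holds for the lack-of-response component, its date and the BSC time origin. The gap is in the text and needs no simulation to establish.

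If BSC is exempt, the comparison is biased toward BSC. The sizes above rest on equal background hazards, response rates borrowed from populations of unstated transfusion status, and every non-responder failing at one date. Under those assumptions the bias is large, and at 36% response it can reverse the apparent order of BSC and drugs that double the time to all other events. Excusing some non-responders reduces it.

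If the clause applies to BSC, the rule is even-handed, but the endpoint then mainly measures response, which BSC is not designed to produce, and stable untransfused patients count as failures. The misfit with 12 months is conditional on that coding; it may equally mean that the historical figure was built on another definition.

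The rule must be settled before EFS is used for adaptation or analysis.

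**What to change.** For the Part II comparison with BSC:
1. Measure EFS from randomization in all four arms and assess events on one calendar schedule.
2. State whether, and at what landmark from randomization, lack of response counts in each arm, and whether stable disease and clinical-benefit cases are failures.
3. Base the primary BSC comparison, or at minimum a prespecified companion, on events that every arm can have: transfusion requirement, progression, AML and death. Report it with and without lack of response, loss of response (which only responders can incur) and discontinuation for side effects (which needs study drug).
4. Reconcile the event lists in Sections V, VII and XII, and the two-cycle and six-course passages. Reconcile also the Section VII statement that two-cycle response feeds the adaptive randomization with Section XII, where EFS does so in both parts.
5. Re-check the 12-month historical median against the chosen event set and re-run Table 6.

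The cost is protocol wording, new simulations and event assessment of BSC patients on the common calendar. The Part II endpoint may then differ from Part I, and the reference median may need restating.
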